#### 2.3.2.1. Binary Secondary Endpoints in Double-Blind Phase

For binary endpoints such as adapted JIA ACR 30/50/70/90/100 response at each double-blind phase visit, the estimand also uses composite strategy (Estimand 2) and includes the following 5 attributes:

- Population: sJIA patients, as defined by the inclusion criteria for the double-blind phase, who are randomized.
- Treatment: tofacitinib 5 mg BID, placebo

- Variable: binary endpoints such as aJIA ACR 30/50/70/90/100 response at each double-blind phase visit through Week 52.

Patients who complete study participation after maintaining JIA ACR inactive disease for at least 24 weeks (clinical remission) in the double-blind phase, and patients who are still active in the double-blind withdrawal phase of the study but have to discontinue before Week 52 due to study end, will use the last on-treatment windowed visit ([Appendix 3.13](#)) ACR value (ie, last observation carried forward (LOCF)), from that visit onward until Week 52 visit.

Patients who discontinue from the investigational product for any other reasons before Week 52 are considered as treatment failure, ie, ACR non-responders, from that visit onward until Week 52 visit. If there is an on-treatment ACR assessment that falls within the same windowed visit with the investigational product discontinuation, the ACR assessment will prevail.

- Intercurrent event: investigational product discontinuation will be the intercurrent event. The intercurrent event is captured through the variable definition. Data collected after discontinuation of the investigational product (ie, off-treatment data) will not be included to derive the endpoint, ie, only on-treatment data ([Appendix 3.13](#)) collected prior to or at Week 52 visit will be used.
- Population-level summary: difference in proportion of subjects achieving binary endpoint response such as aJIA ACR 30/50/70/90/100 response at each double-blind phase visit through Week 52 between those assigned to tofacitinib at randomization versus those assigned to placebo at randomization.

Estimands for all other binary secondary endpoints except occurrence of disease flares in double-blind phase will follow the same composite strategy as the above secondary estimand. See endpoint definitions in [Section 3.2.1](#) and [Appendix 1](#) and missing data handling in [Section 5.3](#) for specific differences.

For occurrence of disease flare at each double-blind phase visit through Week 52, the estimands follow the estimands for the primary endpoint of time to sJIA disease flare in the double-blind phase as in [Section 2.3.1](#) and [Section 2.3.3](#).

### 2.3.2.2. Continuous Secondary Endpoints in Double-Blind Phase

For change from open-label baseline in each sJIA ACR core variable, except for disability index from the CHAQ for which change from double-blind baseline will be considered (i.e., change from OL baseline in number of joints with active arthritis, number of joints with limited range of motion, physician global evaluation of disease activity, parent/legal guardian/subject evaluation of overall well-being [from the CHAQ] and ESR; and change from DB baseline in disability index from the CHAQ) at each scheduled visit through Week

52 in the double-blind phase, the estimand uses treatment policy strategy (Estimand 3) and includes the 5 attributes below:

- Population: sJIA patients, as defined by the inclusion criteria for the double-blind phase, who are randomized.
- Treatment: tofacitinib 5 mg BID, placebo
- Variable: change from open-label baseline in each sJIA ACR core variable, except for disability index from the CHAQ for which change from double-blind baseline will be considered, at each scheduled visit through Week 52 in the double-blind phase.
- Intercurrent event: the intercurrent event of investigational product discontinuation will not be considered. All the data collected while On- and Off-investigational product until Week 52 will be used to derive the endpoints.
- Population-level summary: the mean difference in change from open-label baseline in each sJIA ACR core variable, except for disability index from the CHAQ for which change from double-blind baseline will be considered, at each scheduled visit through Week 52 in the double-blind phase between all those assigned to tofacitinib at randomization and all those assigned to placebo at randomization.

Estimands for all the other secondary continuous endpoints in double-blind phase ([Section 3.2.1](#)) will follow the hypothetical estimand defined in [Section 2.3.4](#).

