In the double-blind withdrawal phase of the study, “responders” from Part 1 and Part 2 of the open-label phase will be randomized in a 1:1 ratio to either continue tofacitinib or start placebo. The primary endpoint of the study is time to sJIA flare in the double-blind phase. The double-blind withdrawal phase will continue until a sufficient number of flares are reported as described in Section 11.

The Sponsor will use external Centralized Coordinating Centers to review and confirm applicable real-time assessments of efficacy, including the Adapted JIA ACR 30/50 response, sJIA flare, and inactive disease status (JIA-ACR). The Coordinating Centers will also monitor and offer recommendations on corticosteroid tapering of study participants. Refer to [Section 8.1.12](#) for details on the coordinating centers. The Centralized Coordinating Centers will be blinded to study drug assignment in the double-blind withdrawal phase of the study.

All subjects participating in this study, including those who discontinued in the open-label or double-blind phase, will have the option, if eligible (based on inclusion and exclusion criteria), of enrolling in the tofacitinib JIA long-term extension study (A3921145) after completion of this study.

[figure not shown]
Subjects who flare in the double-blind withdrawal phase will be given the opportunity to participate in A3921145 and be treated with open-label tofacitinib. Subjects who achieve ACR clinical remission (ie, maintain JIA ACR inactive disease during 24 consecutive weeks) will complete their participation in A3921165 and be given the opportunity to enter A3921145.

Subjects who discontinue Investigational Product in the double-blind phase and who do not enter A3921145 will continue in A3921165 for follow up of efficacy and safety endpoints. Subjects will be required to perform all scheduled visits until Week 52 after randomization or until the study concludes, whichever comes first. Subjects should receive standard-of-care treatment in accordance with local treatment guidelines.

Subjects who discontinue the study in the Open-Label Phase and do not enter A3921145, will be required to perform a follow-up visit 28 days after the last dose of study treatment.

A schematic of the study design is shown below:

Figure 2. Study Design

a Subjects <40 kg will receive an equivalent weight-based lower dose of tofacitinib 5 mg BID.

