6.8. End of Study or Early Termination Visit

Each subject's participation in the study will end once the subject experiences a first sJIA flare in the double-blind phase or 24 consecutive weeks of inactive disease (clinical remission). An end-of-study visit should be performed.

Subjects who are not able to maintain an Adapted JIA ACR 30 response for 4 weeks in the open-label phase, or who have fever due to sJIA lasting more than 2 consecutive days in Part 1, or who fail CS tapering more than twice in Part 2 of the open-label phase will need to be discontinued from the study.

Subjects will have the option, if eligible (based on inclusion and exclusion criteria), of enrolling in the tofacitinib JIA long-term extension study (A3921145) after withdrawal or completion of this study.

- Subjects who discontinue investigational product in the double-blind phase and who do not enter A3921145 will be required to continue in the study and perform all scheduled visits until Week 52 after randomization or until the study concludes, whichever comes first. Such subjects should transition to standard-of care treatment in accordance with local guidelines.
- Subjects who discontinue in the Open-Label Phase and do not enter A3921145 will be required to return for a follow up visit 28 days after the last dose of study treatment.

The study will be completed once the requisite number of subjects have reported flare in the double-blind withdrawal phase (refer to [Section 11](#)). At that time and upon notification by the Sponsor, the investigator will be required to schedule an end-of-study visit for all remaining active subjects.

If a subject discontinues from the study at a regularly scheduled study visit, all assessments and procedures for that visit should be completed. In addition, a Tanner stage assessment should be done as part of the study termination. If a subject discontinues outside of a regularly scheduled visit, an Early Termination visit should be scheduled as soon as possible. The procedures and assessments listed below will be performed at the End of Study or Early Termination visit.

Subjects should be instructed to fast, if possible, for lipid panel testing.

- Review concomitant medications. Refer to [Section 5.8](#).
- Complete physical exam, including skin examination for chickenpox or shingles. **Country specific amendment for EU sites (including UK):** a full skin cancer examination must be performed as part of the complete physical examination.

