### 2.3.3. Additional Estimands for Primary Endpoint

A supplementary (Estimand 4) estimand for the primary endpoint will use the hypothetical strategy, which estimates the treatment effect if all patients adhere to the protocol and the intercurrent event of investigational product discontinuation has not occurred. It differs from the primary estimand in the following 2 attributes:

- Variable: time to sJIA disease flare in the double-blind phase.

Patients who discontinue from investigational product for reasons other than flare in the double-blind phase and who complete study participation after achieving clinical remission, will be considered as non-flare and censored at the last available flare assessment while on investigational product. (More details of on-treatment censoring time and risk period are provided in [Section 5.3.1.1](#).)
- Intercurrent event: all data after an intercurrent event (investigational product discontinuation), if collected, will be excluded.

A second supplementary estimand (Estimand 5) for the primary endpoint will use the treatment policy strategy and estimate the treatment difference regardless of whether an intercurrent event occurs. It differs from the primary estimand in the following 2 attributes:

- Variable: time to sJIA disease flare in the double-blind phase.

- Intercurrent event: investigational product discontinuation is not considered for analysis. All the flare data collected both on-treatment and off-treatment in the double-blind phase of Study A3921165 will be used. For subjects who withdraw from study early, before reaching 52 weeks of double-blind treatment from Study A3921165 and enrolled in the LTE (Study A3921145), the flare data collected through Week 52 post randomization from both studies A3921165 and A3921145 will be included (see [Section 6.1.2.1](#)). (More details of on-study censoring time and risk period are provided in [Section 5.3.1.1](#).)

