## 5. GENERAL METHODOLOGY AND CONVENTIONS

### 5.1. Hypotheses and Decision Rules

The primary null hypothesis in this study is that there is no difference between the distributions of time to disease flare in the double-blind randomized withdrawal phase between tofacitinib and placebo. The alternative hypothesis is that, among the subjects that meet the randomization criteria, time to disease flare is increased in the subjects remaining on tofacitinib in the double-blind withdrawal phase versus placebo subjects.

The difference between the distributions of time to disease flare will be tested using an unstratified log-rank test ([Schoenfeld, 1987](#); [Shih, 1999](#); [Yang, 2012](#)).

There will be potentially 2 planned analyses. The First Analysis will be performed after 28 subjects have reported flare in the double-blind phase. Number of flares required for the 2 planned analyses will be counted according to the definition of having a flare in the primary estimand ([Section 2.3.1](#)). The purpose of the First Analysis is to allow early stopping of the study for efficacy or futility, and to assess safety of tofacitinib. The investigators, subjects, and sponsor study team will remain blinded to treatment assignment in the double-blind phase through the entire duration of the trial until final database release.

If the study does not end for efficacy or futility at the First Analysis, a total of 37 subjects with flares will be required for the Final Analysis to yield an overall power of 80% using a log-rank test to detect the treatment difference, assuming a 1-sided type-I error rate of 2.5% and a 64% improvement in median time to flare (i.e., a hazard ratio of 0.36 and a median time to flare of 236 days for placebo; assumptions based on a similar sJIA randomized withdrawal trial). The number of flares needed at the Final Analysis will be based upon the actual number of flares at the First Analysis (additional details are provided below and in [Appendix 2](#)).

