To protect the integrity of the study and to preserve the type I error rate at 0.025 (1-sided test) and overall study power at 80% (type II error rate  $\beta=0.2$ ), a fraction of  $\alpha$  for efficacy and a fraction of  $\beta$  for futility will be spent at the First Analysis and accounted for in the overall type I error rate and type II error rate, respectively. A formal efficacy boundary for rejecting the null hypothesis is constructed by using the spending function methodology of the gamma family design with  $\gamma= 4$ . Similarly, a formal futility boundary for not rejecting the null hypothesis is constructed by using the spending function methodology of the gamma family design with  $\gamma= -4$ .

- If the value of the test-statistic at the First Analysis crosses the efficacy boundary ( $z \leq -1.973$ , 1-sided  $p \leq 0.0242$ ), the trial may be stopped for efficacy.
- If the value of the test-statistic at the First Analysis crosses the futility boundary ( $z \geq -1.240$ , 1-sided  $p \geq 0.1074$ ), the trial may be stopped for futility.
- Otherwise, the trial will continue as planned. The Final Analysis will be performed after flares have been reported in 37 subjects.

**Table 2. Efficacy and Futility Stopping Boundaries with 28 Flares at First Analysis Expressed as Hazard Ratio, Z Scores and P-values**

Efficacy Stopping Boundary				
	Number of Flares	Hazard Ratio	Z-score	P-value (1-sided)
First Analysis	28	0.474	-1.973	0.0242
Final Analysis	37	0.427	-2.586	0.0049
Futility Stopping Boundary				
	Number of Flares	Hazard Ratio	Z-score	P-value (1-sided)
First Analysis	28	0.626	-1.240	0.1074

**Table 2. Efficacy and Futility Stopping Boundaries with 28 Flares at First Analysis Expressed as Hazard Ratio, Z Scales and P-values**

Final Analysis	37	0.427	-2.586	0.0049
----------------	----	-------	--------	--------

Assuming a hazard ratio of 0.36 (tofacitinib vs placebo) and a median time to flare of 236 days for placebo Randomization ratio = 1:1, type I error rate (1-sided) = 2.5%, power = 80.4%

Efficacy boundary: gamma family spending function with  $\gamma = 4$

Futility boundary (non-binding): gamma family spending function with  $\gamma = -4$

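### The core-variable analysis is labelled treatment policy to Week 52, but the plan does not secure core-variable values after a flare, so for flared children it nearly reduces to the on-product analysis

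*SAP*

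**What the plan says.** **Estimand.** SAP 2.3.2.2 compares all children assigned to each arm at every visit through Week 52, and disregards product discontinuation: "All the data collected while On- and Off-investigational product until Week 52 will be used to derive the endpoints". SAP 6.2.1.2 and Table 4 repeat this. They leave missing values to the MMRM of SAP 5.2.3, without imputation. Estimand 7 (SAP 2.3.4) is the on-treatment counterpart.

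**Follow-up after flare.** Protocol 6.8 says of each child that "participation in the study will end once the subject experiences a first sJIA flare in the double-blind phase". Protocol 3.3 and 8.1.8 agree. Protocol 3.3 and 6.7.1 require visits to Week 52 only for children who stop product for a reason other than flare and do not roll over. Protocol 3.1, by contrast, says that children who stop product in the double-blind phase and "who do not enter A3921145 will continue in A3921165 for follow up of efficacy and safety endpoints", with no exception for flare. The Protocol Summary, Schedule of Activities footnote 25, Protocol 7.1, a bullet in Protocol 6.8 and SAP 2.2 read the same way.

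**Extension data.** For time to flare (Estimand 5), SAP 2.3.3 says that "the flare data collected through Week 52 post randomization from both studies A3921165 and A3921145 will be included". No such sentence exists for Estimand 3.

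**Choice of Week 52.** SAP 2.3.2 (and Protocol 10.2.2) justify it by expecting more than half of the children to complete 52 weeks.

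**The concern.** A treatment policy estimand needs outcomes after product is stopped. In a withdrawal trial these matter most for children who flare. If their values end at the flare visit, the stated estimand is not what the analysis estimates. The Week 52 difference would depend on a model assumption about the children in whom withdrawal failed, with unequal missingness between arms. The tipping-point analyses in SAP 6.1.2.2 cover only time to flare, so no planned analysis tests that assumption for the core variables.

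**Working it through.** **1. Which children have later core-variable values in Estimand 3?**

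| Child | After the event | Values available to Estimand 3 |
|---|---|---|
| Flares, enters A3921145 | Leaves A3921165 | None named |
| Flares, does not enter | Protocol 3.3, 6.7.1, 6.8, 8.1.8: ends after the end-of-study visit. Summary, footnote 25, 3.1, 7.1: visits to Week 52 | None, or yes, depending on which passages govern |
| Stops for another reason, does not enter | Visits to Week 52 or study end | Yes |
| Stops for another reason, enters A3921145 | Leaves A3921165 | None named (flare data only, Estimand 5) |
| Clinical remission | Completes A3921165 | None named |

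The flare visit normally falls within the last dose plus 2 days, which SAP Appendix 3.13 counts as on-treatment. For a child whose data end there, Estimands 3 and 7 use nearly the same observations.

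**2. Reproduce the plan's design figure.** SAP 5.1 assumes "a hazard ratio of 0.36 and a median time to flare of 236 days for placebo". It also gives equal allocation, a one-sided alpha of 0.025, a stated power of 80.4%, 28 flares at the First Analysis and 37 at the end: "The Final Analysis will be performed after flares have been reported in 37 subjects".

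- Drift = |ln 0.36| × √d / 2: 2.70 at 28 flares and 3.11 at 37.
- Alpha spent at the First Analysis = 0.025 × (1 − e^(−4×28/37)) / (1 − e^(−4)) = 0.0242.
- Result: efficacy z −1.973, futility z −1.240, final z −2.586, power 80.4%. All match SAP Table 2.

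**3. Check the time-to-flare model.** Take exponential times, placebo median 236 days and hazard ratio 0.36. Protocol 10.1.1 gives 23 children randomized over 225 weeks, then 0.315 per week to 54. The model gives 20.1 flares at week 262 and 40.0 at week 358. The protocol states 262 and 358 weeks for its 20 and 40 flares, so the model reproduces the plan's own projection.

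**4. Share with an event by day d.** Placebo: 1 − exp(−ln 2 × d/236). Tofacitinib: 1 − exp(−0.36 × ln 2 × d/236).

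| Day | Placebo | Tofacitinib |
|---|---|---|
| 168 (Week 24) | 38.9% | 16.3% |
| 350 (day before the Week 52 window opens) | 64.2% | 30.9% |
| 364 (Week 52) | 65.7% | 31.9% |

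With 54/2 = 27 per arm, day 364 gives 0.657 × 27 = 17.7 placebo and 0.319 × 27 = 8.6 tofacitinib children.

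**5. Completion of 52 weeks.** Event-free at day 364: 34.3% placebo and 68.1% tofacitinib, average 51.2%. At the 37-flare cut, about 79.6% of the 54 have been randomized long enough to reach day 364. Observed shares become 0.796 × 34.3% = 27.3% and 0.796 × 68.1% = 54.2%, average about 41%. Separately, if 10% to 40% of event-free children left for remission (an assumption; the documents give no rate), the shares would be 31% to 21% placebo and 61% to 41% tofacitinib, before study-end loss.

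**6. How far the placebo figure depends on every event being a flare.** If a fraction f of placebo events are non-flare stops kept in follow-up, the observed share is 0.343 + f × 0.657. It reaches one half at f = (0.5 − 0.343)/0.657 = 0.24 (0.22 at day 350), with no other loss.

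**The case against.** Five stronger readings are tempting, and the documents do not support them.

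- *No flared child has any later value.* All core variables are recorded at the flare or end-of-study visit, and several passages would keep a flared child who does not roll over in the study to Week 52. No roll-over rate is given.
- *Most placebo Week 52 values will certainly be missing.* The primary event is composite: product stops other than for remission or study end count as flares. Non-flare stops without roll-over stay in follow-up, and no split is given. The 66% is an upper figure for loss through events, not a forecast.
- *The MMRM simply fills in values from children on product.* The SAP says data are not imputed, and the model conditions on each flared child's worsened value at the flare visit. What stands is that the later course is estimated under missing at random, largely from children still on product.
- *The extension linkage is already planned for these children.* SAP 6.1.2.1 describes it for children who stop for reasons other than flare. That flare is derived there suggests the components are collected, but the A3921145 protocol is not available to confirm it.
- *The regulator asked for exactly these data.* SAP Table 1 cites regulatory feedback for the change to treatment policy, but not its content.

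It is also fair that these are by-visit secondary endpoints, that the primary analysis is unaffected, and that projected loss at Week 24 is smaller. None of this makes the label fit the data that the plan secures.

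**Conclusion.** The mismatch holds. Followed as written, the plan gives an Estimand 3 that for flared children differs little from Estimand 7. For children who enter A3921145 this is so whichever protocol passages govern; for those who do not, it depends on an unresolved contradiction.

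Projected loss of Week 52 values is up to about 66% of placebo and 32% of tofacitinib children (39% and 16% by Week 24). This assumes exponential times, the planning median and hazard ratio, every event a flare, and no values after flare. Remission and study end would add to it; non-flare stops kept in follow-up would reduce it. The direction of bias cannot be determined from the documents. On the same inputs, the expected majority completing 52 weeks is 51% before those exits and about 41% at the 37-flare cut. The point should be acted on, but it does not threaten the primary result.

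**What to change.** 1. In SAP 2.3.2.2, 6.2.1.2 and Table 4, state that Estimand 3 includes A3921145 core-variable values through Randomization Day + 378, and that re-treatment with open-label tofacitinib is part of the policy. Extend the linkage to flared children after confirming that the components are collected there. If they are not, relabel the estimand.
2. Add a missing-not-at-random sensitivity analysis for the core variables. Imputation from off-product donors is not a safe substitute: with about 27 per arm, enough donors cannot be assumed.
3. Reconcile Protocol 3.3, 6.7.1, 6.8 and 8.1.8 with the Protocol Summary, Schedule of Activities footnote 25, Protocol 3.1 and 7.1, and SAP 2.2 on follow-up after flare. Which rule applies is for the sponsor to settle.
4. Correct the statement in SAP 2.3.2 on completing 52 weeks, and its counterpart in Protocol 10.2.2.

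The cost is SAP wording, some added data linkage, one further analysis and a protocol clarification. The treatment difference may shrink, because placebo children who enter A3921145 restart tofacitinib. Estimand 7 remains as the on-product view.
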